#### 8.2.2.1 Definition of Response.

For the purposes of this study, complete remission (CR) will be defined as achieving a morphologic leukemia free state by achieving all of the following criteria: bone marrow myeloblasts  $< 5\%$  by morphologic assessment; AND absence of circulating blasts with phenotypic or morphologic features of leukemia (e.g. Auer rods) AND no evidence of extramedullary disease. For subjects with  $\leq 5\%$  blasts but possessing flow cytometric, cytogenetic or molecular aberration (Sec 5.1); CR will also require resolution (absence) of that aberration. Partial remission (PR) will be defined as a  $\geq 50\%$  reduction in bone marrow blast percentage to 5-25% or marrow blasts  $< 5\%$  with persistent Auer rods, flow cytometric or cytogenetic disease. PR is not possible response designation for individuals entering with  $\leq 5\%$  blasts. SD will be defined as  $\leq 5\%$  increase in blasts or decreased blast percentage in the bone marrow that does not meet the criteria for PR. Progression will be defined as  $>5\%$  increase in bone marrow blast percentage from prior bone marrow aspirate. NOTE Given these patients have relapsed after allogeneic HCT blood count recovery is not considered at criteria for response in this protocol.

8.2.3 Stopping rules for futility: Study subjects will receive pembrolizumab  $\pm$  the addition of standard chemotherapy, therefore stopping rules for futility are not indicated. The primary endpoint of this study is safety and feasibility.

8.2.4 Stopping rules for toxicity: Patients will be monitored closely for the development of immune-mediated toxicity that may be attributable to pembrolizumab. For the purposes of this trial, we will consider the development of acute GvHD as a distinct entity from the known immune-mediated toxicity profile associated with PD1 blockade, though there may be clinical overlap. The impact of PD1 blockade on the development of acute GvHD following allogeneic HCT has not been studied in human subjects. Therefore, a rational approach will focus on whether there is an **increase** in the rates and severity of

acute GvHD and other immune mediated toxicities over the expected baseline. The following assumptions will be used to assess potential toxicities associated with this trial:

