- All subjects will be inherently at risk for the development of GvHD as this study is limited to patients who have relapsed post-HCT. Although screening will exclude patients with active GvHD requiring immunosuppression, subjects will remain at risk independent of whether they receive study drug. The expected incidence of clinically significant grade 2 to 4 acute GvHD (requiring therapy) without Pembrolizumab is estimated to be 40-50%.
- Patients who relapse (without GVHD present) may still be receiving standard immunosuppression post-HCT to reduce the risk of inciting GVHD. Immunosuppressive medications (IS) may be withdrawn or tapered per usual care. Because patients are at risk for the development of GVHD within several weeks after IS withdrawal tapering may occur during administration of pembrolizumab at a rate determined by the treating physician. Due to timing of IS withdrawal overlapping with the treatment period for pembrolizumab, potentially confounding its relationship to the study drug, an aggregate summary of toxicity will be used to determine whether PD1 blockade is potentially associated with an increase in the severity of acute GvHD.
- For the purposes of this study, toxicity will be deemed as excessive if 12 of 20 subjects (60%) develop severe acute GvHD ( $\geq$  grade 3-4) OR  $\geq$  grade 3 immune related adverse events that do not improve to grade 1 after systemic corticosteroid treatment for 14 days. This study specific stopping rule is intended to capture excessive rates of severe acute GvHD (grades 3-4) as an adverse safety signal. We have set this threshold because some degree of GvHD is an anticipated consequence of usual withdrawal of immune-suppression and chemotherapy which is a current treatment standard for relapse. Grade 2 GvHD is associated with less morbidity and mortality compared to grades 3-4 and may be a potential surrogate of a beneficial anti-leukemic response (GvL), thus grade 2 GvHD will be recorded but not included in the stopping definition. The occurrence of severe acute GvHD for this toxicity rule will be monitored during the induction treatment period until 30 days after the last induction treatment dose of pembrolizumab given for the induction phase (doses 1-4).

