- We will also make interim assessments after 10 and 15 patients have been observed for 30 days after the last induction dose of pembrolizumab. Specifically, further accrual will be halted if we observe at least 6 of 10 or 9 of 15 patients developing severe acute GvHD. If the true rates of severe acute GvHD are 30%, 40%, 50% or 60%, the study has respective probabilities of 0.05, 0.18, 0.43, and 0.71 of stopping early.
- 

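### The 10- and 15-subject looks count severe acute GvHD only, while the 12-of-20 excessive-toxicity criterion at the same 60% limit also counts steroid-refractory immune events

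*Combined protocol and SAP*

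**What the plan says.** Three parts of section 8.2.4 (Stopping rules for toxicity) bear on this point.

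- **Aim.** The opening paragraph directs monitoring at an increase in "acute GvHD and other immune mediated toxicities over the expected baseline". It also treats acute GvHD as distinct from the known immune-mediated toxicity of PD-1 blockade, while allowing that the two may overlap clinically.
- **Final criterion.** "toxicity will be deemed as excessive if 12 of 20 subjects (60%) develop severe acute GvHD", or grade 3 or higher "immune related adverse events that do not improve to grade 1 after systemic corticosteroid treatment for 14 days". The next sentence says that this stopping rule "is intended to capture excessive rates of severe acute GvHD (grades 3-4) as an adverse safety signal". The observation window is given for GvHD only: "The occurrence of severe acute GvHD for this toxicity rule will be monitored during the induction treatment period", and on to 30 days after the last induction dose.
- **Interim looks.** The plan will also make "interim assessments after 10 and 15 patients have been observed for 30 days after the last induction dose of pembrolizumab", and "further accrual will be halted if we observe at least 6 of 10 or 9 of 15 patients developing severe acute GvHD". For true severe GvHD rates of 30%, 40%, 50% and 60% it gives "respective probabilities of 0.05, 0.18, 0.43, and 0.71 of stopping early".

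Section 3.1.1 includes clinically significant immune-mediated toxicity in the primary objectives, together with GvHD. Section 8.2.3 names safety and feasibility as the primary endpoint.

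**The concern.** The three boundaries look like one rule applied at three sample sizes, since 6/10, 9/15 and 12/20 are all 60%. But the event changes between them. The final count has two limbs and the interim counts have one. Because section 8.2.4 separates GvHD from immune-mediated toxicity, the interim wording cannot be taken to include immune events silently.

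At stake is a primary safety outcome. Suppose 3 of the first 10 subjects have severe GvHD and 3 others have refractory immune events. Then 6 of 10, or 60%, have had an event that the final criterion counts, but the look sees 3 and passes. The printed stopping probabilities also describe only the GvHD limb, so a reader cannot tell from them how the trial would behave if immune toxicity were the main problem.

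**Working it through.** **Inputs.** Boundaries 6/10, 9/15 and 12/20, true rates 30% to 60%, and the printed probabilities, all from section 8.2.4. The documents give no rate for refractory immune events, so 5% to 30% is an assumption. A 20% severe GvHD rate is also an assumption; 30% is a rate that the plan itself uses.

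**1. Reproduce the plan's figures.** With p the event rate and X10, X15 the cumulative counts,

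P(early halt) = P(X10 ≥ 6) + P(X10 ≤ 5 and X15 ≥ 9).

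| p | first look | second look | total | printed |
|---|---|---|---|---|
| 0.30 | 0.0473 | 0.0037 | 0.0510 | 0.05 |
| 0.40 | 0.1662 | 0.0200 | 0.1863 | 0.18 |
| 0.50 | 0.3770 | 0.0526 | 0.4295 | 0.43 |
| 0.60 | 0.6331 | 0.0763 | 0.7094 | 0.71 |

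The printed values are those of the two looks. The only difference is that 0.186 rounds to 0.19, not 0.18.

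**2. Composite rate.** Let g be the severe GvHD rate and i the refractory immune-event rate. The share of subjects with either event is

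- max(g, i) under complete overlap,
- 1 − (1 − g)(1 − i) if independent,
- g + i with no overlap (the upper bound).

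For example, g = 0.30 and i = 0.10 give 1 − 0.70 × 0.90 = 0.37 if independent, and 0.40 with no overlap.

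**3. Early-halt probability if the composite were counted at 6/10 and 9/15.** The formula is that of step 1, with the composite rate as p.

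| g | as written | overlap case | i = 5% | 10% | 20% | 30% |
|---|---|---|---|---|---|---|
| 0.30 | 0.05 | independent | 0.09 | 0.13 | 0.27 | 0.46 |
| 0.30 | 0.05 | no overlap | 0.10 | 0.19 | 0.43 | 0.71 |
| 0.20 | 0.007 | independent | 0.02 | 0.04 | 0.12 | 0.27 |
| 0.20 | 0.007 | no overlap | 0.02 | 0.05 | 0.19 | 0.43 |

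Under complete overlap nothing changes for either g up to i = 20%.

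**4. The extreme case at 15 subjects.** Take 8 subjects with severe GvHD (5 of the first 10, then 3 of the next 5) and 4 others with refractory immune events. The composite is 8 + 4 = 12, the number in the final criterion. Neither look is triggered, because 5 < 6 and 8 < 9. The chance of at least 12 composite events among 15 with both looks passed follows from the same binomials. Each subject without GvHD has an immune event with probability i (independent) or i/(1 − g) (no overlap). At g = 0.30 the result is at most 0.011 for i up to 20%. At i = 30% it is 0.013 (independent) to 0.073 (no overlap).

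**The case against.** A reader might infer from step 4 that accrual would carry on after the trial's own excessive-toxicity count had been reached. The documents do not establish that. Section 8.2.4 calls the 12-subject criterion a stopping rule and introduces the looks as additional to it. Nothing says that the criterion is dormant until subject 20, so 12 composite events among 15 subjects may already halt accrual. The text does not say either way, and the scenario is rare. What remains is narrower: no limit that counts immune events operates below 12.

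A second objection is that GvHD-only looks may be what the sponsor meant. The intent sentence names severe GvHD, the window is stated for GvHD, and the 60% threshold is justified by the GvHD expected after withdrawal of immunosuppression. On that reading the immune-event limb of the 12-of-20 criterion is the outlier. This has force. It does not remove the inconsistency, but it means that the composite is the better-supported reading and not the only one.

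Third, the counted immune event is narrow, overlap with GvHD is acknowledged, and the larger differences need 20% or more of subjects to be affected. That is correct.

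Fourth, other safeguards exist: the adverse-reaction termination criterion (section 5.8), monthly review by two committees (sections 10.5.2 and 10.5.3), expedited reporting (section 7.2.3.1) and individual discontinuation rules (Table 3). They reduce the risk, but none sets a number at which accrual halts.

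**Conclusion.** The point holds as an inconsistency in the stopping rule. Section 8.2.4 uses a two-limb event for 12/20 and a one-limb event for 6/10 and 9/15 at the same 60% limit. This follows from the text without any assumed rate. As written, refractory immune events cannot trigger either look, and no numerical limit includes them until 12 composite events have accumulated.

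The size depends on rates that the documents do not give. At 30% severe GvHD with independent immune events, the early-halt probability is 0.05 as written, against 0.09, 0.13 and 0.27 at immune-event rates of 5%, 10% and 20%. The printed probabilities are not in error for the event they name, apart from the rounding at 40%. The matter should be fixed because safety is primary and the correction is cheap. Confidence is moderate, because the text leaves open which event was intended and whether 12 events stop accrual at once.

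**What to change.** Reconcile section 8.2.4 to one event and one observation window for all three counts. The option that best fits the primary objectives and the 12-of-20 criterion is the composite:

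- count each subject once, for either limb, at 6/10, 9/15 and 12/20, with the same window for both limbs;
- state that reaching 12 composite events at any time halts accrual;
- restate the early-stopping probabilities as 0.05, 0.19, 0.43 and 0.71 at composite rates of 30%, 40%, 50% and 60%;
- state how an immune event still within its 14 steroid days is counted at a look, a question that arises only once immune events count there;
- align the sentence on the rule's intent.

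If a GvHD-only rule is intended, remove the immune-event limb from the 12-of-20 criterion and say so.

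The cost is wording and one relabelled line of probabilities, with no extra subjects or assessments. The composite has two downsides. One is a higher chance of halting early: at 30% severe GvHD, 0.05 becomes 0.13 with 10% independent immune events. The other is a possible delay of up to 14 days at a look, if the look waits for an event to be classified.

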## 9.0 LABELING, PACKAGING, STORAGE AND RETURN OF CLINICAL SUPPLIES

### 9.1 Investigational Product

The investigator shall take responsibility for and shall take all steps to maintain appropriate records and ensure appropriate supply, storage, handling, distribution and usage of investigational product in accordance with the protocol and any applicable laws and regulations.

Clinical Supplies will be provided by Merck as summarized in Table 7.

**Table 7 Product Descriptions**

Product Name & Potency	Dosage Form
pembrolizumab 50 mg	Lyophilized Powder for Injection
pembrolizumab 100 mg/ 4mL	Solution for Injection

## **9.2 Packaging and Labeling Information**

Clinical supplies will be affixed with a clinical label in accordance with regulatory requirements.

## **9.3 Clinical Supplies Disclosure**

This trial is open-label; therefore, the subject, the trial site personnel, the Sponsor and/or designee are not blinded to treatment. Drug identity (name, strength) is included in the label text; random code/disclosure envelopes or lists are not provided.

## **9.4 Storage and Handling Requirements**

Clinical supplies must be stored in a secure, limited-access location under the storage conditions specified on the label.

Receipt and dispensing of trial medication must be recorded by an authorized person at the University of Michigan.

Clinical supplies may not be used for any purpose other than that stated in the protocol.

## **9.5 Returns and Reconciliation**

The investigator is responsible for keeping accurate records of the clinical supplies received from Merck or designee, the amount dispensed to and returned by the subjects and the amount remaining at the conclusion of the trial.

Upon completion or termination of the study, all unused and/or partially used investigational product will be destroyed per institutional policy. It is the Investigator's responsibility to arrange for disposal of all empty containers, provided that procedures for proper disposal have been established according to applicable federal, state, local and institutional guidelines and procedures, and provided that appropriate records of disposal are kept.

# **10.0 ADMINISTRATIVE AND REGULATORY DETAILS**

## **10.1 Confidentiality**

Subject medical information obtained as part of this study is confidential, and must not be disclosed to third parties, except as noted below. The subject may request in writing that medical information be given to his/her personal physician.

The Investigator will permit direct access to source data and documents by the FDA and/or other applicable regulatory authority. The access may consist of study-related monitoring, audits, IRB or Ethics

Committee reviews, and FDA inspections. Release of research results should preserve the privacy of medical information and must be carried out in accordance with Department of Health and Human Services Standards for Privacy of Individually Identifiable Health Information, 45 CFR 164.508.

## **10.2 Compliance with Financial Disclosure Requirements**

The sponsor, investigator and members of the study team will comply with all applicable regulations regarding financial disclosure requirements.

## **10.3 Compliance with Law, Audit and Debarment**

The study will be conducted in accordance with U.S. Food and Drug Administration (FDA) and International Conference on Harmonization (ICH) Guidelines for Good Clinical Practice (GCP), the Declaration of Helsinki, Health Canada, any applicable local health authority, and Institutional Review Board (IRB) or Ethics Committee requirements.

This study must have the approval of a properly constituted IRB or Ethics Committee. Before the investigational drug is shipped to the Investigator, the Investigator or designee will provide Merck with a copy of the IRB or Ethics Committee approval letter stating that the study protocol and any subsequent amendments and informed consent form have been reviewed and approved.

The Investigator or designee will be responsible for obtaining annual IRB or Ethics Committee re-approval throughout the duration of the study.

The Investigator is also responsible for notifying their IRB or Ethics Committee of any significant adverse events that are serious and/or unexpected. The Investigator is also required to notify the FDA in writing of any SAE that is both unexpected and related to the study drug, within 15 days of knowledge of the event, and within 7 days of a death related to the study drug.

## **10.4 Compliance with Trial Registration and Results Posting Requirements**

Under the terms of the Food and Drug Administration Modernization Act (FDAMA) and the Food and Drug Administration Amendments Act (FDAAA), the Sponsor of the trial is solely responsible for determining whether the trial and its results are subject to the requirements for submission to the Clinical Trials Data Bank, <http://www.clinicaltrials.gov>. Information posted will allow subjects to identify potentially appropriate trials for their disease conditions and pursue participation by calling a central contact number for further information on appropriate trial locations and trial site contact information.

## **10.5 Quality Management System**

The following quality management systems at the University of Michigan will be performed in the conduct of this clinical trial.

### **10.5.1 Data Safety Monitoring Plan**

The following are the procedures for data and safety monitoring of this clinical trial to be conducted at the University of Michigan Blood and Marrow Transplant program and sponsored by Merck, Inc. This is to ensure the safety of participants, the validity of research data, and the appropriate termination of studies for which significant benefits or risks have been uncovered or when it appears that the trial cannot be

concluded successfully. This protocol will conduct a data and safety monitoring process as described in the plan below.

### **10.5.2 Clinical Monitoring Plan**

This trial will be monitored in accordance with the NCI approved University of Michigan Comprehensive Cancer Center Data and Safety Monitoring Plan.

The study team will provide continuous review of the data and patient safety and meet monthly or more frequently depending on the activity of the protocol. The discussion will include matters related to the safety of study participants (SAE/UaP reporting), validity and integrity of the data, enrollment rate relative to expectations, characteristics of participants, retention of participants, adherence to the protocol (potential or real protocol deviations) and data completeness. At these regular meetings, the protocol specific Data and Safety Monitoring Report form will be completed and signed by the Principal Investigator or by one of the co-investigators.

Data and Safety Monitoring Reports will be submitted to the University of Michigan Comprehensive Cancer Center Data and Safety Monitoring Committee on a monthly basis for independent review.

The University of Michigan Comprehensive Cancer Center Data and Safety Monitoring Committee can request a 'for cause' audit of the study if the committee identifies a need for a more rigorous evaluation of study-related issues. A "for cause" audit would be conducted by the Quality Assurance Review Core (QARC) of the University of Michigan Comprehensive Cancer Center.

A regulatory authority (e.g. FDA) may also wish to conduct an inspection of the study, during its conduct or even after its completion. If an inspection has been requested by a regulatory authority, the site investigator must immediately inform the Clinical Trials Office that such a request has been made.

### **10.5.3 Trained and Certified Personnel**

All of the research protocol personnel who will work with study subjects, study subject data or subjects' research samples have completed training in the protection of human research participants per guidelines issued by the U. S. Department of Health and Human Services, Office of Human Research Protections. The documentation of completion of the certification is maintained in the Oncology Clinical Trials Support Unit (OCTSU). The investigator and designated associates have attended an IRB sponsored HIPAA research presentation in accordance with the policy of the study site. Each participant in this research trial will be listed by study specific numbers, without initials or date of birth; however, the date of transplant may be included when corresponding with the IRB or outside agencies.

**Designation of Responsibilities:** The Principal investigator is solely responsible for the implementation, conduct and safety of human subjects enrolled in this trial. The principal investigator has however, designated associates to assist with the protocol implementation which includes but is not limited to the following:

1. BMT Physicians – have been designated to assist with participant education, informed consent process, study implementation and compliance, recording of primary source documentation, AE assessment and reporting, adherence to all regulations.

2. BMT Research Nurse(s) - have been designated to assist with participant education, informed consent process, study implementation and compliance, recording of primary source documentation and adherence to all regulations.
3. BMT Data Manager(s) - have been designated to assist with patient enrollment/eligibility, verification of protocol compliance, all data collection and recording from primary source, AE reporting, DSM reports and adherence to all regulations.
4. BMT Clinical Team - The members of the BMT clinical team that have been designated to assist the investigator in any aspect of this protocol will be listed on the protocol specific designation log.
5. The BMT program's internal Data and Safety Monitoring Committee (BMT DSMC) will meet monthly to review the data, safety and monitoring reports and all SAEs that have been filed.

### **Storage and Dissemination of Reports**

The Oncology Clinical Trials Support Unit (OCTSU) at the University of Michigan is responsible for collating all the Data and Safety Monitoring Reports and providing this information to Data Safety Monitoring Committee. The OCTSU will coordinate the reporting process between the Investigators, the Sponsor, the IRB and UMCCC DSMC as well as other applicable reporting agencies (FDA and study sponsors). Copies of all related correspondence and reporting documents will be maintained in a locked file by the OCTSU regulatory team and the research data file will be maintained in a file by the BMT data management team.

